6.3.7 ACUTE GVHD RESPONSE ALLOWING FOR APPROVED NEXT-LINE THERAPY

This endpoint focuses upon the effect of the randomized treatment (AAT or PTM) on acute GVHD response, possibly in conjunction with an approved next-line therapy. The proportions of patients with CR, PR (including the subset with VGPR), and treatment failure (TF) will be described at Days 7, 14, 21, 28, 56, and 86 post-randomization. The designation of TF consists of patients with NR, MR, and acute GVHD progression. The Day 86 response will be summarized only in patients remaining on study maintenance treatment (AAT/PTM) after Day 28. Patients who die, initiate next-line GVHD therapy that is not approved by the protocol chairs, or have escalation of prednisone-equivalent steroid

dose to 2.5mg/kg/day or more prior to an acute GVHD assessment will be classified as non-responders (NR) at the corresponding Day with the following exception: if a patient received a prednisone-equivalent dose of 2.5mg/kg/day or more on the randomization day, maintaining this starting dose is not automatically considered an NR, but escalation to a dose higher than the starting one is an NR; moreover, if their dose is tapered below 2.5 mg/kg/day and later re-escalated to 2.5 mg/kg/day or above, they will be classified as an NR. Patients with a missing acute GVHD assessment will be classified as non-responders (NR) at the corresponding Day. The acute GVHD assessment conducted out of window (refer to Section 7.1 for visit window definition) will be considered as missing.

Note that this endpoint uses the same ITT population for analysis as the secondary endpoint defined in section 6.3.6, while the categorization of response for patients who receive a protocol chair approved next-line therapy differs between these two endpoints. The receipt of an approved next-line therapy will be categorized as a failure (NR) for the endpoint in 6.3.6, while for this secondary endpoint 6.3.7 the receipt of an approved next-line GVHD therapy is not automatically considered a failure (NR) and, consequently, such a patient is still assessed for GVHD response as specified in Section 6.1.

6.3.8 SYSTEMIC INFECTIONS

The incidence of Grade 2 to 3 systemic infections occurring from randomization until 30 days after the last dose of the study drug (AAT or PTM) will be described. Grade 2 to 3 systemic infections are defined according to BMT CTN Manual of Procedures (MOP). Death before infection will be treated as a competing risk. Infection time is defined as the time from the date of randomization until the documented date of infection onset or death from any cause, whichever happens first. The outcome type is defined as shown in Table 11. All infections and deaths occurring on or after the randomization date will be included. Patients who are alive and free of infection onset at the time of analysis will be censored at the last day known to be alive or at the analysis data freeze date, whichever is earlier. Patients experiencing event(s) after the analysis cut-off date will be censored at the analysis cut-off date.

Table 11: Systemic Infections Competing Risks Definition

Situation	Date of Event or Censoring	Outcome
Infection occurred before or on analysis cutoff date	Date of infection onset	Infection
Death without prior infection onset occurred before or on analysis cutoff date	Date of death	Death
Death and/or infection onset occurred, all events happened after analysis cutoff date	Analysis cutoff date	Censored
No death or infection onset occurred, last known date alive is before or on analysis cutoff date	Last known date alive	Censored
No death or infection onset occurred; last known date alive is after analysis cutoff date	Analysis cutoff date	Censored

Time of Infection = Date of Event or Censoring – Date of Randomization + 1

6.3.9 ADVERSE EVENTS

The incidence of Grade 3-5 treatment-emergent adverse events occurring from randomization until 30 days after the last dose of study drug (AAT or PTM) will be described, where the grade is defined per Common Terminology Criteria for Adverse Events (CTCAE) Version 5.0.

6.3.10 CHRONIC GVHD

Chronic GVHD is defined per the 2014 NIH Consensus Criteria (Jagasia et al. 2015), with death before chronic GVHD treated as a competing risk. Chronic GVHD time is defined as the time from the date of randomization until the documented date of chronic GVHD onset of any severity (mild, moderate, severe, or unknown) or death from any cause, whichever happens first. All chronic GVHD onsets and deaths occurring on or after the randomization date will be included. Patients who are event-free at the time of analysis will be censored at the last day known to be alive or at the analysis data freeze date, whichever is earlier. Patients experiencing event(s) after the analysis cut-off date will be censored at the analysis cut-off date.

Table 12: Chronic GVHD Competing Risks Definition

Situation	Date of Event or Censoring	Outcome
Chronic GVHD onset occurred before or on analysis cutoff date	Date of chronic GVHD onset	Chronic GVHD
Death without prior chronic GVHD onset occurred before or on analysis cutoff date	Date of death	Death
Death and/or chronic GVHD onset occurred, all events happened after analysis cutoff date	Analysis cutoff date	Censored
No death or chronic GVHD onset occurred, last known date alive is before or on analysis cutoff date	Last known date alive	Censored
No death or chronic GVHD onset occurred, last known date alive is after analysis cutoff date	Analysis cutoff date	Censored

Time of chronic GVHD = Date of Event or Censoring – Date of Randomization + 1

6.3.11 RELAPSE/PROGRESSION OF THE PRIMARY DISEASE

A relapse/progression of the primary disease is defined as in section 6.3.4. Death without prior relapse/progression is treated as a competing risk for relapse/progression. Relapse/progression time is defined similarly as PFS time in section 6.3.4, with the outcome type defined as shown in Table 8. All relapses/progressions and deaths occurring on or after the randomization date will be included. Patients who are event-free at the time of analysis will be censored at the last day known to be alive or at the analysis data freeze date, whichever is earlier. Patients experiencing event(s) after the analysis cut-off date will be censored at the analysis cut-off date.

6.4 EXPLORATORY ENDPOINTS

6.4.1 SERUM AAT LEVELS

AAT levels will be assessed using measurements of serum antigen concentration and serum AAT concentration with functional activity (functional AAT concentration) just prior to infusion and 30 min (+/- 15 min) post-end of infusion on Day 0 and on Days 16, 28, and 56 post-treatment initiation; these levels will also be assessed prior to infusion on Days 8 and 24 post-treatment initiation. Ctrough value is the serum AAT concentration of the sample collected prior to drug infusion and Cmax value is the serum AAT concentration of the sample collected within 15 to 45 minutes post-end of infusion. Post-infusion measurements are limited to subjects receiving a dose of AAT/PTM.

6.4.2 STOOL AAT LEVELS

Stool concentrations of AAT at baseline and at Days 8 and 28 post-initiation of treatment (or at treatment discontinuation (TD) if before Day 28) will be collected at a subset of centers for a limited cohort of patients.

6.4.3 IMMUNE CELL SUBSETS

Peripheral blood ratios of T regulatory to T effector (Treg/Teff) cells and Natural Killer (NK) cell populations will be assessed at baseline and on Days 16, 28, and 56 post-treatment initiation (or at treatment discontinuation (TD) if before Day 56).

6.4.4 INFLAMMATORY CYTOKINES AND GVHD BIOMARKERS

Serum levels of IL-1 β , IL-6, IL-10, TNF α , amphiregulin (AREG), heparin sulfate, ST2, and REG3 α will be evaluated at baseline and at Days 8, 28, and 56 post-treatment initiation (or at treatment discontinuation (TD) if prior to Day 56).

6.4.5 OVERALL AND ORGAN SPECIFIC RESPONSE RATES BY GVHD AND BIOMARKER-BASED RISK CLASSIFICATIONS

The proportions of patients with an overall response (complete or partial) at Day 28 post-randomization will be described by the MN risk category (high vs. standard) and by Ann Arbor biomarker risk score (1 vs. 2 vs. 3). Additionally, the response rate of each GVHD target organ will be described on Day 28 by treatment arm, MN risk and Ann Arbor biomarker risk. An organ overall response is defined as a decrease in its staging from baseline, along with being alive, free of any next-line GVHD therapy, and free of escalation of prednisone-equivalent steroid dose to 2.5mg/kg/day or more. The baseline staging refers to the maximum GVHD organ staging within 72 hours prior to enrollment. Patients who have an escalation of prednisone-equivalent steroid dose to 2.5mg/kg/day or higher will be classified as a non-responder with the following exception: if a patient received a prednisone-equivalent dose of 2.5mg/kg/day or more on the randomization day, maintaining this starting dose is not automatically considered a non-response, but escalation to a dose higher than the starting one is an non-response; moreover, if their dose is tapered below 2.5 mg/kg/day and later re-escalated to 2.5 mg/kg/day or above, they will be classified as an non-response. Patients will be classified as responders or non-responders for each target organ accordingly. Organ staging is performed by MAGIC criteria, shown in Table 6. Patients with a missing Day 28 acute GVHD assessment will be classified as non-responders for all organs. The Day 28 acute GVHD assessment

conducted out of window (refer to Section 7.1 for visit window definition) will be considered as missing. The organ-specific response rate will be evaluated only using patients with a staging greater than 0 in the corresponding organ at baseline.

The Ann Arbor biomarker risk score (Levine et al. 2015) will be computed from baseline levels of TNFR1, ST2, and REG3 α . The algorithm is as follows:

- For each patient, compute their estimated 6 month non-relapse mortality risk \hat{p} according to
$$\log(-\log(1 - \hat{p})) = -9.169 + 0.598 \log_2 TNFR1 - 0.028 \log_2 REG3\alpha + 0.189 \log_2 ST2$$
- If $\hat{p} \leq 10\%$, biomarker score = 1; else if $\hat{p} \geq 40\%$, biomarker score = 3; else, biomarker score = 2

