2.5.1.7 Dose and Administration

The first dose of study drug (AAT/PTM) **must be initiated as soon as possible after enrollment and must be within 12 hours of enrollment**. Each dose of study drug will be 120 mg/kg (actual weight) based on the patient's weight recorded at enrollment. Subsequent doses should be given on Days 4, 8, 12, 16, 20, 24, 28 (Table 2-1). **The patient's weight recorded at enrollment will be used to determine the dose for all infusions** (i.e., dose adjustments for changes in weight during the treatment period will not be made).

Patients that are non-responders or progress will be considered to be steroid-refractory (SR) and may start next-line therapy as described in section 2.5.3.3. Ruxolitinib is recommended for next-line therapy as it is an FDA-approved treatment for SR-GVHD.

Responding patients (CR/PR) at Day 28, compared to maximum GVHD organ staging within 72 hours prior to enrollment, that are receiving study drug alone, or study drug plus ruxolitinib, should continue to receive treatment at a dose of 120 mg/kg (actual weight) on Days 35, 42, 49, and 56 (Table 2-1). Patients who are not in CR/PR at Day 28 will not continue to receive study drug. Responding patients at Day 28 who progress after Day 28 may continue to receive weekly doses through Day 56.

Patients that receive next-line therapy other than ruxolitinib may not continue receiving study drug unless approval is granted by the BMT CTN 1705 Protocol Chairs.

Table 2-1 Study Drug Schedule

	Day											
	0 ¹	4	8	12	16	20	24	28	35	42	49	56
All patients	X	X	X	X	X	X	X	X				
CR/PR (VGPR) patients only									X	X	X	X

¹ Enrollment is Day 0, First dose of study drug must occur within 12 hours after enrollment and may fall on Day 0 or Day 1.

Patients can receive study drug (AAT/PTM) as either an inpatient or outpatient. All subsequent treatments will have a window of \pm 3 days to allow for efficient scheduling of patients for holidays/weekends/etc. Following administration of the first or second dose, adjusting future infusions to accommodate a Monday/Thursday or Tuesday/Friday schedule is encouraged.

Infusion Rate: AAT/ PTM should be administered at a rate not exceeding 0.08 mL/kg body weight/minute. If adverse events occur, the rate should be reduced, or the infusion interrupted until the symptoms subside. The infusion may then be resumed at a rate tolerated by the subject.

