3.1.1 Response Definitions

Response definitions are listed below:

1. Complete Response (CR) is defined as a score of 0 for the GVHD staging in all evaluable organs.
2. Partial response (PR) is defined as improvement in one or more organs involved with GVHD symptoms without progression in others.
 - a. Very good partial response (VGPR) is defined as a quantitative and functional response that closely approximates CR. Patients must have all of the following clinical features. i.e., (1) no rash or rash involving < 25% of body surface area (BSA) without bullae (residual faint erythema and hyperpigmentation do not count), (2) serum bilirubin < 2mg/dl or < 25% of baseline at enrollment and (3) ability to tolerate food or enteral feedings with predominantly formed stool (no overt GI bleeding or cramping and no more than occasional nausea or vomiting).
3. Mixed response (MR) is defined as improvement in one or more organs with deterioration in another organ manifesting symptoms of GVHD or development of symptoms of GVHD in a new organ.
4. No Response (NR) is defined as absence of any improvement or progression as defined.
5. Progression is defined as deterioration in at least one organ without any improvement in others.

Patients who receive next-line systemic GVHD therapy (or escalation of steroids to ≥ 2.5 mg/kg/day of prednisone [or methylprednisolone equivalent of 2 mg/kg/day]) before Day 28 will be classified as NR. **Responses categorized as NR, MR and progression will be treated as a failure for the primary endpoint.**

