3.3.4 Inflammatory Cytokines and GVHD Biomarkers

Serum levels of IL-1 β , IL-6, IL-10, TNF α , amphiregulin (AREG), HS, ST2, and REG3 α will be evaluated at baseline and at Days 8, 28, and 56 post-initiation of treatment (or at treatment discontinuation (TD) if prior to Day 56). Remaining samples will be retained for analysis of additional relevant cytokines, DAMPs and GVHD biomarkers.

3.3.5 Overall and Organ-Specific Response Rates by Refined Minnesota Risk and Biomarker-Based Risk Classifications

The proportions of patients with an overall response (complete or partial) at Day 28 post-randomization will be described by Refined Minnesota risk category (high or standard risk) and by Ann Arbor biomarker risk score (1, 2, or 3). Additionally, the response rate of each GVHD target organ will be described at Day 28 by Refined Minnesota risk and Ann Arbor biomarker risk. An organ response is defined as a decrease in staging of that organ from baseline. The organ-specific response rate will be evaluated only using patients with a staging greater than 0 in the corresponding organ at baseline.

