5.1.2 Randomization

Following enrollment, patients will be stratified by centers and randomized within each center in a 1:1 ratio using permuted blocks of random sizes for the two treatment arms.

Treatment practices differ considerably by centers. This includes the time to declare a patient refractory to steroids and potentially initiate next-line therapy. The variability by center may produce greater differences in treatment groups compared with age (adolescent vs adult), GVHD risk or disease. Additionally, the pathobiology of GVHD in both adolescent and adult and in malignant and non-malignant disease patient populations are similar. Therefore, since the presentation of GVHD and the anticipated response to treatment are expected to be similar, center was prioritized as the primary stratification variable.

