- No response (NR) is defined as the absence of improvement or progression in any organ.
- Progression is defined as deterioration in at least one organ without any improvement in others.

Patients who die will be classified as non-responders (NR). Patients who have an escalation of prednisone-equivalent steroid dose to 2.5mg/kg/day or higher will be classified as NR with the following exception: if a patient received a prednisone-equivalent dose of 2.5mg/kg/day or more on the randomization day, maintaining this starting dose is not automatically considered an NR, but escalation to a dose higher than the starting one

is an NR; moreover, if their dose is tapered below 2.5 mg/kg/day and later re-escalated to 2.5 mg/kg/day or above, they will be classified as an NR.

The receipt of next-line GVHD therapy also may impact how a patient is classified for GVHD response. This affects the following endpoints as described:

- **Overall Response at Day 28, Duration of Response, Acute GVHD Response to AAT/PTM, Overall and Organ Specific Response Rate by GVHD and Biomarker-based risk Classifications:** If a patient receives next-line GVHD therapy prior to a GVHD assessment visit, they will be classified as a non-responder (NR) for that assessment time.
- **Acute GVHD Response Allowing for Approved Next Line Therapy:** If a patient receives next-line GVHD therapy that is not approved by the protocol chairs prior to a GVHD assessment visit, they will be classified as a non-responder (NR) for that assessment time. However, the receipt of protocol chair-approved next-line therapy has no impact on the grading of GVHD response for this endpoint.
- **GVHD-free Survival:** If a patient receives next-line GVHD therapy while being event-free, they will be classified as an event at the time point of the therapy's initiation.

6.2 PRIMARY ENDPOINT – OVERALL RESPONSE AT DAY 28

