7.11 CHANGES TO PROTOCOL-SPECIFIED ANALYSIS

The current SAP elaborates on the protocol-specified analysis. The sole change in the SAP from the protocol-specified analysis is that the significance level of the two-sided testing of exploratory endpoints is planned to change from 5% to 1%. Any future revisions to the SAP that constitute changes from the protocol-specified analysis, and the justification for these changes, will be documented here.

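### The SAP adds survival, next-line-therapy and steroid conditions to the protocol's organ-specific response and does not list this as a change, so one rescue fails every involved organ in a descriptive exploratory table

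*SAP*

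**What the plan says.** Protocol 3.3.5 gives organ response its own one-line definition: "An organ response is defined as a decrease in staging of that organ from baseline". It evaluates each organ only in patients with a stage above 0 in that organ at baseline. It sets no condition on survival, next-line therapy or steroid dose.

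SAP 6.4.5 defines it differently: "An organ overall response is defined as a decrease in its staging from baseline, along with being alive, free of any next-line GVHD therapy". It further requires that steroids were not escalated to a prednisone-equivalent 2.5 mg/kg/day or more. It also counts a missing or out-of-window Day 28 assessment as non-response in all organs. SAP 6.1 lists the organ-specific endpoint by name among those for which next-line therapy before the visit means non-response.

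On reporting, SAP 6.4.5 says that "the response rate of each GVHD target organ will be described on Day 28 by treatment arm, MN risk and Ann Arbor biomarker risk". SAP 7.6.5 compares organ rates across levels of Minnesota risk and Ann Arbor score with Fisher's exact test. Its by-arm subgroup and interaction analyses concern overall response only.

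SAP 7.11 then states: "The sole change in the SAP from the protocol-specified analysis is that the significance level of the two-sided testing of exploratory endpoints" moves from 5% to 1%.

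**The concern.** The endpoint is there to show which organs respond. Next-line therapy is a decision about the whole patient. Protocol 2.5.1.7 says: "Patients that are non-responders or progress will be considered to be steroid-refractory (SR) and may start next-line therapy". A patient whose rash goes from stage 3 to stage 0, but whose gut worsens and who then starts ruxolitinib, is a skin responder under the protocol and a skin non-responder under the SAP.

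Organ rates under the SAP therefore mix organ behaviour with rescue use. Protocol 5.1.2 says treatment practice differs considerably between centers and adds: "This includes the time to declare a patient refractory to steroids and potentially initiate next-line therapy". If AAT helps one organ and so reduces rescue, organs on which it has no effect will also look better in the AAT column. A reader of the SAP alone would not know that the definition departs from the protocol, because SAP 7.11 says there is only one change.

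**Working it through.** **The plan's own figures.** Neither document states a figure for organ response. The nearest design figure is the primary comparison in Protocol 5.2: 50% vs 75%, 68 per arm, one-sided 2.5%, power 86%. With the pooled rate 0.625, the critical difference is 1.96 × √(2 × 0.625 × 0.375 / 68) = 0.163, as in Protocol Table 5-1. The standard error under the alternative is √((0.25 + 0.1875)/68) = 0.0802. Power is Φ((0.25 − 0.163)/0.0802) = 86.2%, so the design figure reproduces.

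**Formulas.** For one organ, let
- s = stage-decrease rate in patients not given next-line therapy, the same in both arms (no true AAT effect on this organ);
- sr = stage-decrease rate in patients given next-line therapy;
- qP, qA = next-line use before Day 28 in the PTM and AAT arms. Death and steroid escalation act in the same way and could be added to q.

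SAP rate = s(1 − q), so the AAT − PTM difference is s(qP − qA).

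Protocol rate = s(1 − q) + sr·q, so the difference is (s − sr)(qP − qA).

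**Range.** All inputs are assumptions: s = 60% to 80%, qP = 25% to 35%, qA = 10% to 20%.

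| Case | SAP, PTM vs AAT | SAP difference |
|---|---|---|
| s = 60%, q = 25% vs 20% | 45.0% vs 48.0% | +3 points |
| s = 70%, q = 35% vs 20% | 45.5% vs 56.0% | +10.5 points |
| s = 80%, q = 35% vs 10% | 52.0% vs 72.0% | +20 points |
| any s, qP = qA | equal | 0 |

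Over the same range, where qP − qA runs from 5 to 25 points, the stage-only difference is:
- 0 if sr = s;
- 0.20 × 0.05 to 0.20 × 0.25 = +1 to +5 points if sr is 20 points below s;
- −0.15 × 0.05 to −0.15 × 0.25 = −0.75 to −3.75 points if sr is 15 points above s.

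**Tied to the design rates.** Assume gut response is 50% vs 75% (the documents give these as overall rates), s = 70%, and 50%, 70% or 90% of gut failures are rescued. Then q is 25% vs 12.5%, 35% vs 17.5%, or 45% vs 22.5%. The SAP skin rates are 52.5% vs 61.3%, 45.5% vs 57.8%, and 38.5% vs 54.3%: gaps of about 9, 12 and 16 points with no skin effect.

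**How visible it would be.** With s = 70%, next-line use 35% vs 20%, and 30 to 60 skin patients per arm (assumed), the observed skin rate favours AAT in about 76% to 85% of simulated trials. Without the artefact it would be under half, by symmetry and allowing for ties.

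**The planned risk-group comparison.** The same algebra applies to Minnesota risk. In Protocol Table 1-1, pooling both sources and converting percentages to counts, Day 28 response is 27/49 for stage 1 lower GI plus skin (standard risk) and 25/61 for stages 2 to 4 plus skin (high risk). Non-response is then 22/49 = 44.9% and 36/61 = 59.0%. With 70% skin stage decrease in both groups and 50% to 90% of non-responders rescued (assumed), the SAP rule alone gives a skin difference of 0.70 × (0.590 − 0.449) × 0.5 to 0.9, or about 5 to 9 points.

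**The case against.** **The SAP rule is deliberate and coherent.** Protocol 3.1.1 already classes patients given next-line therapy before Day 28 as non-responders, SAP 6.1 extends this to the organ endpoint by name, and SAP Table 16 uses the same composite strategy for the primary endpoint. It stands that the composite is a legitimate estimand. It does not remove the conflict: the Protocol 3.1.1 rule sits among patient-level categories and ends in failure for the primary endpoint, while Protocol 3.3.5 defines organ response separately and without it.

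**Stage-only is not clean either.** It credits ruxolitinib or another agent with an organ's improvement. This stands in full. In the three design-rate scenarios, if 85% of rescued patients have a skin stage decrease (assumed), the stage-only rates are 73.8% vs 71.9%, 75.3% vs 72.6% and 76.8% vs 73.4%, a spurious deficit for AAT of about 2 to 3 points. Ranking stage-only above the composite would be a preference between estimands, so both should be shown.

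**An inflated false-positive rate.** A reader might infer that the rule produces spurious significant organ effects. About 34 skin patients per arm is a reasonable guess (68 × 110/217, the share of the eligible Table 1-1 rows with skin involvement). A two-sided 5% test between arms would then reject in 11%, 16% and 24% of trials in the three scenarios. The SAP plans no such test, and SAP 7.1 sets exploratory tests at 1%. Fisher's exact test at that level would reject in 1.8%, 3.6% and 6.5%. The distortion is in described rates, not in a planned claim.

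**A certain false skin or liver benefit.** A reader might also infer that any gut-only effect must appear in other organs. The documents do not support that. They give no next-line rates and do not say which organ triggers rescue, and the artefact vanishes if next-line use is equal between arms.

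**Conclusion.** The two definitions conflict, and SAP 7.11 is wrong to say that the exploratory significance level is the only change. The direction of the consequence follows from the SAP wording: wherever AAT lowers next-line use through one organ, the SAP's by-arm rates in other organs are shifted in its favour by s(qP − qA). The size, about 3 to 20 points, rests on assumed stage-decrease and rescue rates, on no true effect in the organ concerned, and on the same s in both arms. It concerns only patients who have that organ involved and are rescued.

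Severity is minor. The endpoint is exploratory and outside the testing hierarchy, its by-arm organ rates are descriptive, and the primary and secondary endpoints are unaffected.

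**What to change.** 1. In SAP 6.1, 6.4.5 and 7.6.5, report two labelled organ-specific rates, by arm and by risk group: the protocol's stage decrease in that organ, and the rescue-free composite now in SAP 6.4.5. SAP 6.1 must be amended together with 6.4.5, or the two will contradict each other.
2. State that death or missing Day 28 staging counts as non-response in the stage-decrease rate, since Protocol 3.3.5 is silent on both.
3. Show next-line use before Day 28 by arm beside these rates. SAP 7.2.2 already tabulates its initiation before Day 28.
4. Add a note that the stage-decrease rate can credit next-line therapy.
5. List the added composite definition in SAP 7.11 as a change from the protocol. Leave the overall response rule as it is.

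The cost is SAP wording and an extra row per organ. No new data are needed: Protocol 2.5.1.10 keeps patients in follow-up after treatment failure, and Protocol 4.3.2 collects organ staging weekly to Day 56.
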